6 CONVENTION FOR HANDLING PARTIAL AND MISSING DATES

6.1 Handling Partial Dates

6.1.1 Partial Tumor Assessment Dates for PFS

All dates for tumor assessment must be completed with day, month and year.

If one or more measurement dates (e.g. X-ray, CT-scan for target and non-target tumor lesions) are partial but other measurement dates are available, this/these partial date(s) are not considered for calculation of the assessment date.

6.1.2 Partial Dates for Clinical Events

Imputation will be only performed for partial dates in concomitant medication and prior cancer therapy, missing dates (date element is totally unknown) will not be imputed.

The following rules will be used to impute incomplete start and end date:

- Incomplete start date: assign 1 to missing day, January to missing month.
- Incomplete end date: assign the last date of the month (28/29/30/31) to missing day, December to missing month.
- If the imputed stop date is before the start date (imputed or non-imputed start date), then the imputed stop date will be replaced with the start date.

6.1.3 Partial Dates for Adverse Events

No imputation will be applied for adverse events. AE with partial or missing dates will be categorized as treatment emergent unless there was sufficient specificity to the onset date to document that the event began before the first dose of study treatment. Incomplete AE start date as reported will be used to compare with the first dose date of study treatment to distinguish if it is a TEAE. Example: If the first dose date is 01FEB 2013 and incomplete start date for an AE is JAN2013, then this AE will not be treated as TEAE.

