2.1 Study Objectives

2.1.1 Primary Objective

The primary objective is to assess the safety and tolerability of ARQ 087 in subjects with advanced solid tumors (Part 1; Dose Escalation/Food-effect Cohorts) or with advanced solid tumors with FGFR genetic alterations, including intrahepatic cholangiocarcinoma (iCCA) with FGFR2 gene fusion (Part 2; Expanded Cohort, signal finding).

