5.4.7 Analyses of Safety Variables

All analyses for the safety variables will be performed on safety population. Safety variables include adverse events, laboratory parameters, vital signs, ECOG performance status, 12-lead ECG and physical exams.

Descriptive statistics will be calculated for quantitative safety data, frequency counts and percentages will be compiled for classification of qualitative safety data. All percentages will be calculated based on the number of subjects in the safety population, unless otherwise indicated. Baseline is defined as the last non-missing value prior to the first dose date or on day 1, unless otherwise noted.

Adverse Events

Adverse events will be evaluated for severity using NCI-CTCAE, version 4.03. AE summaries will include treatment-emergent adverse events (TEAEs).

A TEAE is defined as:

- an AE which is not present prior to the first dose of ARQ 087 and started after taking the study drug during the treatment period or within 30 days after the last dose of the study drug;
- an AE which is present prior to the first dose of ARQ 087 and increased in severity after taking study drug during the treatment period or within 30 days after the last dose of study drug;
- an AE which is considered study drug-related regardless of the start date of the event.

All TEAEs will be coded using Medical Dictionary for Regulatory Activities (MedDRA[®]) Version 15.1 and summaries will be presented by system organ class and preferred term. Separate TEAE summaries will be generated for the following categories:

- All TEAEs
- Severe TEAEs (Grade 3 or higher)
- SAEs
- TEAEs related to study drug
- TEAEs leading to treatment discontinuation
- TEAEs leading to treatment interruption
- TEAEs leading to treatment interruption then dose reduction
- TEAEs resulting in death
- TEAEs listed according to maximum severity
- TEAEs classified as DLTs

TEAEs will be summarized by presenting the number and percentage of subjects having at least one TEAE in each system organ class and preferred term. A subject with multiple occurrences of the same TEAE will be counted only once in the AE category.

Separate TEAE summaries will be presented by system organ class, preferred term, and maximum CTCAE 4.03 grade. A subject with multiple CTCAE grades for the same TEAE will be summarized under the maximum CTCAE grade recorded for the event.

Laboratory Test

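### SAP 6.1.3 classifies adverse events with incomplete start dates on onset alone, in conflict with the worsening and drug-related criteria of the TEAE definition in SAP 5.4.7

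*SAP*

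**What the plan says.** SAP 5.4.7 gives three separate grounds on which an AE is treatment-emergent:

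1. New onset: "an AE which is not present prior to the first dose of ARQ 087 and started after taking the study drug", during treatment or within 30 days after the last dose.
2. Worsening: "an AE which is present prior to the first dose of ARQ 087 and increased in severity after taking study drug", over the same period.
3. Relatedness: "an AE which is considered study drug-related regardless of the start date of the event".

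SAP 6.1.3 covers AEs whose dates are partial or missing. No date is imputed. The default is inclusive: "AE with partial or missing dates will be categorized as treatment emergent unless there was sufficient specificity to the onset date" shows a start before first dose. The test is that the incomplete start date "as reported will be used to compare with the first dose date of study treatment to distinguish if it is a TEAE". The worked example takes first dose as 01FEB2013 and concludes that if the "incomplete start date for an AE is JAN2013, then this AE will not be treated as TEAE".

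Section 6.1.3 mentions neither worsening nor relatedness, and neither section says which prevails.

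**The concern.** The second and third criteria exist to keep events whose onset lies before first dose. A rule that removes an event because its onset lies before first dose works against both, and it contradicts the third criterion in terms.

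Two programmers could set the TEAE flag differently for one record, one following the example in 6.1.3 and the other the definition in 5.4.7. For a worsened event, the result would turn on whether the site had recorded the day of onset, which has no bearing on whether the drug made the condition worse.

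Safety and tolerability are the primary objective (SAP 2.1.1), and SAP 5.4.7 sets out its AE tables as TEAE summaries. They include Grade 3 or higher events, SAEs, drug-related events, events leading to discontinuation and DLTs. A record that fails the flag would leave every one of these tables for which it otherwise qualified.

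**Working it through.** The plan states no figure on this point, so the check sets the two rules side by side, using the SAP's own first-dose date of 01FEB2013.

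**Step 1: which incomplete dates are excluded by 6.1.3?**

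| Recorded onset | Result |
|---|---|
| Missing | TEAE by default |
| 2013 (year only) | TEAE, since the date does not show a pre-dose start |
| FEB2013 | TEAE, for the same reason |
| JAN2013 | Not a TEAE (the SAP's example) |
| 2012 (year only) | Not a TEAE, by the same logic |
| 15JAN2013 (complete) | 6.1.3 does not apply; 5.4.7 governs |

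Only a partial date lying wholly before first dose leads to exclusion.

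**Step 2: for those dates, do the two sections agree?**

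| Worsened on drug | Judged drug-related | 5.4.7 | 6.1.3 read literally | Agree? |
|---|---|---|---|---|
| No | No | Not a TEAE | Not a TEAE | Yes |
| Yes | No | TEAE (criterion 2) | Not a TEAE | No |
| No | Yes | TEAE (criterion 3) | Not a TEAE | No |
| Yes | Yes | TEAE (criteria 2 and 3) | Not a TEAE | No |

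They disagree in 3 of the 4 combinations. With the complete date 15JAN2013, all three of those combinations are TEAEs.

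**Step 3: which of the three can realistically occur?**

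- Related but not worsened: protocol 8.7.1 requires a related AE to follow drug administration in a reasonable time sequence, and 8.7.2 classes an AE without that sequence as not related. An onset month wholly before first dose nearly rules this case out.
- Worsened, related or not: this remains possible. The worsening can follow drug administration even though the original onset did not. The documents do not say which onset date a site enters when a baseline condition worsens.

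**Step 4: the upper time limit.** Section 6.1.3 has no counterpart to the 30-day limit in criterion 1, so an unrelated new event with a partial date beyond that limit would count as a TEAE. Protocol 8.2 and 8.5 end AE capture with the 30-day follow-up, and 5.7 allows the visit only 3 days either side. This case is nearly empty too.

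**Step 5: what one misclassified subject would do to a table row.** The Middle Dose Group combines two cohorts of 3–6 subjects (SAP Table 1 and 3.1.1), so 6–12 in all. The Expanded Cohort plans about 50–60.

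- Middle Dose Group: 1/12 = 8.3 points to 1/6 = 16.7 points.
- Expanded Cohort: 1/60 = 1.7 points to 1/50 = 2.0 points.

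These are the effects of a single subject if a misclassification occurs. They say nothing about how often one would.

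**The case against.** The strongest reply is that 6.1.3 is only a date-handling convention. On that view it settles whether onset fell before or after first dose, and the three-part definition in 5.4.7 then applies as usual. The third criterion, which disregards the start date, would override any start-date comparison. This reading is possible and may be what was intended. It is not what the section says: the stated purpose of the comparison is to decide TEAE status, and the example ends in a final classification with no exception.

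The reply is right on frequency. AE capture begins on the first day of treatment (protocol 8.2), events between consent and dosing are not recorded as AEs (8.1.7), and earlier diagnoses go into medical history (6.1). The conflict needs an on-drug worsening entered as an AE under its original onset, with that date incomplete and wholly before first dose. An excluded event may also still be seen in the listings, since SAP 5.2 lists eCRF data as appropriate.

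A reader might infer that any AE lacking a day of onset can be lost. The documents do not support that: missing dates, and partial dates that could fall on or after first dose, all count as TEAEs.

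**Conclusion.** The inconsistency is real and minor. As written, the two sections give opposite answers for a baseline condition that worsens on drug and carries a month- or year-only onset wholly before first dose. That is the one realistic case.

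A reader might go further and conclude that worsened and drug-related events will drop out of the primary safety tables. The documents do not establish this. The loss depends on 6.1.3 being applied literally and on sites entering the original onset date for a worsened condition, and neither is stated. Nor do they support treating drug-related events without worsening, or events beyond 30 days, as practical sources of error.

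The number of affected records cannot be estimated from the documents and should be small. Of the few AE records that would carry a pre-dose onset, however, many are likely to be worsened events, which criterion 2 was written to keep. With groups as small as 6–12 subjects, it is worth settling the wording before database lock.

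**What to change.** Amend SAP 6.1.3 along these lines:

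*The comparison of a partial start date with the first dose date decides only the first (new-onset) TEAE criterion of Section 5.4.7. The worsening and drug-related criteria apply whatever the completeness of the start date.*

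Change the conclusion of the JAN2013 example to: *not a TEAE unless it worsened on study drug or is considered drug-related.*

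This removes all three conflicting combinations. Events with a documented pre-dose onset that neither worsened nor were judged related stay excluded, as both sections already provide. The cost is two SAP sentences and one added condition in the TEAE flag, with no new data.

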7 INTERIM ANALYSIS

Interim monitoring for futility will be incorporated after response data from 10 subjects with iCCA are available. If objective response is observed in $\geq 30\%$ of enrolled subjects, up to 20

additional subjects with iCCA with FGFR2 fusion will be enrolled, otherwise, the enrollment will be stopped for lack of efficacy.

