## 10 PLANNED STATISTICAL METHODS

The material presented in this section will serve as the basis for the statistical analysis plan. This plan may be revised during the study to accommodate protocol amendments. Because of the nature of this study, no formal statistical analysis is planned. Evaluation of the data will consist primarily of summary displays (e.g., descriptive statistics and graphs).

In addition, for the iCCA sub-cohort of the Expanded Cohort (Part 2), statistical analysis will include interim monitoring for futility. After response data from 10 subjects with iCCA are available, the response rate will be assessed. If the objective response is observed in  $\leq 30\%$  of enrolled subjects, the enrollment will be stopped for lack of efficacy.

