### Best Overall Response: All Time Points

The best overall response is determined once all the data for the subject is known.

*Best response determination in trials where confirmation of complete or partial response IS NOT required:* Best response in these trials is defined as the best response across all time points (for example, a subject who has SD at first assessment, PR at second assessment, and PD on last assessment has a best overall response of PR). When SD is believed to be the best response, it must also meet the protocol specified minimum time from baseline of 8 weeks. If the minimum time is not met when SD is otherwise the best time point response, the subject's best response depends on the subsequent assessments. For example, a subject who has SD at the first assessment, PD at second the assessment, and does not meet the minimum duration for SD, the subject will have a best response of PD. The same subject lost to follow-up after the first SD assessment would be considered inevaluable.

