3.2.4 Efficacy Variables

Best Overall Response (BOR)

The best overall response is determined once all the data for the subject is known. No confirmatory measurement for CR or PR is required in this study. The best overall response is defined as the best response (in the order of CR, PR, SD, and PD) among all overall responses recorded from the start of treatment until the last radiographic tumor assessment (for example, a subject who has SD at first assessment, PR at second assessment, and PD on last assessment has a best overall response of PR). When SD is believed to be the best response, it must also meet the protocol specified minimum time from baseline, 8 weeks (± 3). If the minimum time is not met when SD is otherwise the best time point response, the subject's best response depends on the subsequent assessments. For example, a subject who has SD at first assessment, PD at second and not meeting minimum duration of SD will have a best response of PD. The same subject lost to follow-up after the first assessment would be considered non-evaluable.

Objective Response Rate (ORR)

For purposes of determining the objective response rate (ORR), tumor response will be based on the best overall response recorded for each subject from the date of first dose. The ORR will be calculated as the number of subjects with a complete or partial response divided by the total number of subjects [ORR= (CR+PR)/# subjects].

Disease Control Rate (DCR)

Disease Control Rate (DCR) is defined as the proportion of subjects with the best overall responses of CR, PR and SD [DCR= (CR+PR+SD)/# subjects].

Duration of Objective Response

Duration of objective response is defined as the time from the date of the measurement criteria are first met for CR/PR (whichever is first recorded) until the first date that recurrent or progressive disease is documented.

If a subject is discontinued, dies, or is lost to follow-up with no documentation of progressive disease, duration of response is defined as the time from the date of the first documentation of objective response to the date of the last tumor assessment as a censored value. Duration of response will be measured for responding subjects (PR or CR) only.

Duration of Stable Disease

Duration of stable disease is defined as the time from the start of the treatment until the criteria for disease progression are met.

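### The iCCA futility look sets no minimum follow-up and no rule for subjects still on treatment with stable disease, so running it at its trigger raises the chance of a wrong stop

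*SAP*

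**What the plan says.** The look is triggered by the existence of response data. SAP section 7 has: "Interim monitoring for futility will be incorporated after response data from 10 subjects with iCCA are available". Protocol section 10 puts it this way: "After response data from 10 subjects with iCCA are available, the response rate will be assessed". Protocol section 4.1.2 uses the same trigger, and Protocol section 3 refers simply to the first 10 iCCA subjects. None gives a data cut-off, a minimum follow-up or a number of scans.

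The consequence is worded as binding. SAP section 7 allows expansion at a response rate of 30% or more, and its sentence closes with: "additional subjects with iCCA with FGFR2 fusion will be enrolled, otherwise, the enrollment will be stopped for lack of efficacy".

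The reported objective response rate (ORR) is defined in SAP section 3.2.4, where "tumor response will be based on the best overall response recorded for each subject from the date of first dose". The same section adds: "The best overall response is determined once all the data for the subject is known". Its worked example, shared with Protocol Appendix 6, is "a subject who has SD at first assessment, PR at second assessment, and PD on last assessment has a best overall response of PR".

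Three further provisions matter:

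- Scans are scheduled every eight weeks, the first at C3D1 (Protocol 6.7).
- One cycle of treatment and one post-baseline tumor evaluation make a subject evaluable for response (Protocol 10.3, SAP 4.4).
- CR and PR need no confirmation (SAP 3.2.4, Appendix 6).

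**The concern.** A subject enrolled late among the ten may have a single scan showing SD when the tenth subject's data arrive. That subject can still become a responder at Week 16 or later, and would then count as one in the final ORR. At the look the subject has to be classed somehow, and the plan does not say how. On the ordinary reading, best response recorded so far, the subject adds to the denominator but not to the numerator.

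The error runs in one direction only: response to date cannot exceed final best response. The cutoff is therefore applied to a proportion that is equal to or below the one the trial will report. At stake is whether up to 20 more subjects with FGFR2-fusion iCCA are enrolled, in the population named in the study title.

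**Working it through.** The documents state no error rate or stopping probability for this look, so there is no figure of theirs to reproduce.

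**Inputs from the documents**

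- n = 10 subjects.
- SAP 7 and Protocol 4.1.2 continue at 30% or more, that is 3 or more of 10. Under SAP 7 the look stops at 2 or fewer.
- Protocol 3 and 10 and the synopsis stop at 30% or less, that is 3 or fewer of 10.

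**Assumptions (not in the documents)**

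- p, the final ORR: 0.40 in the main case.
- f, the share of eventual responses already present at Week 8: 0.8 to 0.6, with f = 1 as reference.
- k, the number of the ten with only one scan at the look. The other 10 − k are taken as fully followed. If the look is run as soon as the tenth subject's first scan is in, k is at least 1.

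**Formula.** The count at the look is X = A + B, with A ~ Binomial(k, p·f) and B ~ Binomial(10 − k, p). P(stop) = P(X ≤ 2) under the SAP cutoff and P(X ≤ 3) under the protocol's stop wording.

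**Mature data (k = 0), SAP cutoff:** 0.6^10 + 10(0.4)(0.6^9) + 45(0.4^2)(0.6^8) = 0.0060 + 0.0403 + 0.1209 = 0.167.

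**One subject on a single scan (k = 1), f = 0.8:** p·f = 0.32. For B ~ Binomial(9, 0.4), P(B ≤ 2) = 0.2318 and P(B ≤ 1) = 0.0705. P(stop) = 0.68 × 0.2318 + 0.32 × 0.0705 = 0.180. With f = 0.6 (p·f = 0.24): 0.76 × 0.2318 + 0.24 × 0.0705 = 0.193.

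**All ten on a single scan (k = 10), f = 0.8:** 0.68^10 + 10(0.32)(0.68^9) + 45(0.32^2)(0.68^8) = 0.0211 + 0.0995 + 0.2107 = 0.331. With f = 0.6 the same sum at 0.24 gives 0.556.

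P(stop) at final ORR 40%:

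| Subjects with one scan (k) | SAP cutoff, f = 0.8 | SAP cutoff, f = 0.6 | Protocol stop wording, f = 0.8 | Protocol stop wording, f = 0.6 |
|---|---|---|---|---|
| 0 (or f = 1) | 16.7% | 16.7% | 38.2% | 38.2% |
| 1 | 18.0% | 19.3% | 40.2% | 42.2% |
| 3 | 20.8% | 25.4% | 44.4% | 50.8% |
| 5 | 24.0% | 32.8% | 48.7% | 59.6% |
| 10 (worst case) | 33.1% | 55.6% | 59.6% | 79.9% |

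Responders to date are a subset of final responders, so any group of ten that would stop on mature data also stops at the look. The rise over the first row is therefore the probability that the look stops although the same ten would finally pass. Under the SAP cutoff this is 1.3 to 2.6 points at k = 1, 7.3 to 16.1 at k = 5 and 16.4 to 38.9 at k = 10.

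Other final ORRs, SAP cutoff, f = 0.8 to 0.6:

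| Final ORR | Mature | k = 1 | k = 5 | k = 10 |
|---|---|---|---|---|
| 30% | 38.3% | 39.9-41.5% | 46.6-55.5% | 55.6-73.7% |
| 50% | 5.5% | 6.2-6.9% | 9.8-16.1% | 16.7-38.3% |

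**The case against.** A reader might infer that the documents contradict each other on when response is measured, or that the plan directs late responders to be scored as failures. The text supports neither. The look has no stated time point, so nothing conflicts with the best-response definition, and no sentence says how ongoing SD is scored. On the strictest reading of SAP 3.2.4, such a subject's response is not yet known and the trigger might not be met. The five-subject tumor-type rule does name C3D1, and the iCCA rule beside it does not, which counts against a deliberate first-scan reading.

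A reader might also take the worst-case row as the expected size. That row needs all ten subjects to reach the look with exactly one scan, so essentially all entering within one 8-week interval. The protocol describes iCCA as rare, so staggered entry is more plausible, and earlier subjects' later scans would count. Nor do the documents show that late responses occur. The Food-effect Cohort results in Protocol 4.1.1 give one PR after 8 weeks and one durable SD with at most 26% reduction, which is too little to estimate f.

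Finally, this is signal-finding work without formal hypothesis tests. A stop ends iCCA enrolment only, and later responses in enrolled subjects still enter the ORR.

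All of this stands as a limit on wording and size. It does not close the gap: the rule is binding, its trigger can be met with immature data, and the plan leaves the scoring of those data open.

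**Conclusion.** The point holds as an omission in a binding stopping rule. If the look is run at its trigger on best response to date, subjects on treatment with SD and a single scan count as non-responses, and the chance of wrongly stopping iCCA enrolment can only rise or stay the same. The direction is certain unless every response is visible by Week 8 (f = 1), when the effect is zero. The size is not known, because it depends on f and k. At k = 1 the effect is small; by k = 5 it is large enough to matter for a decision made on ten subjects. The worst-case figures are an upper bound for the stated values of f, not a forecast. This is a low-cost improvement worth making. It is not evidence that the plan requires a Week 8 decision.

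**What to change.** First reconcile the stop at 30% or less (synopsis, Protocol 3 and 10) with the continuation at 30% or more (Protocol 4.1.2, SAP 7). They disagree at exactly 3 of 10, and the cutoff must be defined before the rule below can be applied.

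Then state in SAP 7 and the matching protocol sections:

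- The look is scored on best RECIST 1.1 response (CR or PR) to date, using all scans so far.
- A subject on treatment with SD and no C5D1 (Week 16) scan is pending, not a non-response.
- *Continue* is declared as soon as the number of responders reaches the cutoff.
- *Stop* is declared only when responders plus pending subjects fall short of the cutoff. With a cutoff of 3, for example, one responder and one pending subject is a stop at once (1 + 1 = 2), while two responders and one pending subject must wait (2 + 1 = 3).
- Whether iCCA enrolment pauses or continues while subjects are pending.

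No new scans are needed. The text change is short but touches several sections. A stop may come up to about 8 weeks later, with either a pause or a few more subjects enrolled meanwhile. Responses first seen after Week 16 would still be missed at the look. If none occur that late, P(stop) at final ORR 40% returns to 16.7% under the SAP cutoff, whatever k is.
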